## 3.3 SECONDARY ENDPOINTS ANALYSIS

Efficacy secondary endpoints are described in this section. Non-efficacy secondary endpoints analyses are defined in [Section 3.6.2](#) (AE, SAE), [Section 3.6.3.1](#) (laboratory abnormalities and vital signs), [Section 3.7.1.1](#) (PK) and [Section 3.7.1.2](#) (immunogenicity).

### 3.3.1 Definition of endpoints

The sTSS is the sum of nasal congestion/obstruction, anterior/posterior rhinorrhea, and facial pain/pressure. The total score ranges from 0 to 9 with higher scores indicating greater overall symptom severity. The sTSS will be analyzed as 28-day averages ([Table 8](#)).

### 3.3.2 Main analytical approach

Change from baseline to Week 24 in LMK score and in sTSS comparing dupilumab to placebo will be analyzed on the ITT with screening blood eosinophil count  $\geq 300$  cells/mm^3 population. Handling of IEs will follow that of the primary endpoint. Otherwise, no missing data will be imputed. Descriptive statistics will be provided by intervention group. Mean treatment difference (dupilumab vs placebo) and the corresponding 95% CI (based on the t distribution) will be provided.

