## 8.1 EFFICACY ASSESSMENTS

### 8.1.1 Computerized Tomography Scans using Lund-Mackay

Computerized tomography scans using the LMK allows the assessment of sinus opacification ([37](#)).

The CT scan LMK staging system represents the most widely established method of sinus CT scoring in clinical trials. The LMK total score is based on assessment of the CT scan findings for each sinus area (maxillary, anterior ethmoid, posterior ethmoid, sphenoid, and frontal sinus on each side). The extent of mucosal opacification is rated on a 3-point scale ranging from 0 = normal to 2 = total opacification. In addition, the ostiomeatal complex is graded as 0 = not occluded or 2 = occluded. The maximum score is therefore 12 per side for a maximum total score of 24, corresponding to the sum of all sinuses and the ostiomeatal unit.

This scoring system has been validated in several studies ([37, 38, 39](#)).

The CT scans should be performed anytime during the screening period before first administration of IMP at Visit 2 (baseline CT data), Visit 5 (Week 24). The Visit 7 (Week 52) CT scan is optional due to variable treatment period. Whenever possible a cone beam CT scan should be utilized. In countries for which a specific approval procedure for the CT scan is required by a different committee than the local IEC/IRB, a 4-month window is required between 2 CT scans. If a participant needs to be rescreened or is terminated early from the study intervention, the repeated CT scan or following CT scan must be done over a 4-month restriction window. If Participant who discontinue the study intervention prematurely, the CT scan will be performed as soon as possible, with all other assessments normally planned in EOT Visit as long as between 2 CT scans can meet a 4-month restriction window. Otherwise, the CT scan can be done in next scheduled visit.

It is recommended to avoid use of OCS as rescue therapy during the Week 20 to Week 24 or-the Week 48 to Week 52. If a participant must use OCS during this period to control CRSsNP worsening/acute sinusitis based on Investigator judgment the site should make every efforts to schedule the Week 24 CT scan or the Week 52 CT scan-prior to OCS rescue therapy.

The CT scan will be performed locally and reviewed centrally in a pre-specified manner as described in the Image Acquisition Standards (IAS) and Image Interpretation Standards (IIS) (refer [Section 1.3](#)).

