## 9 STATISTICAL CONSIDERATIONS

### 9.1 STATISTICAL HYPOTHESES

No statistical hypotheses will be tested in this study.

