#### **9.4.3 Secondary endpoint(s)**

- The change from baseline to Week 24 in the secondary endpoints will be analyzed using the same analysis approach as for the primary endpoint. For endpoints comparing dupilumab to placebo, 95% CI of the treatment difference will be provided.

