### 3.2.2 Main analytical approach

The primary endpoint will be analyzed on the ITT with screening blood eosinophil count  $\geq 300$  cells/mm^3 population in the dupilumab group. Intercurrent events (IE) handling strategies are described below:

- The following IE will be handled with the composite strategy:
  - Undergoing sinonasal surgery for CRSsNP or taking SCS for any reason prior to Week 24: data after surgery (actual date) or SCS use will be excluded from the analysis and the worst post-baseline value on or before the time of surgery or SCS use will be used to assign the Week 24 value (ie, WOCF approach). For participants with no post-baseline values, the baseline value will be used.
- The following IEs will be handled with the treatment policy strategy (without IE that need to be handled with composite strategy). Data collected after starting such IEs will be included.
  - Taking other prohibited/rescue medications.
  - Discontinuing the study intervention.

No missing data will be imputed. Descriptive statistics (number of participants, mean, SD, median, minimum and maximum) and 95% CI of the mean (based on the t distribution) in the dupilumab group will be provided.

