## 3.9 CHANGES TO PROTOCOL-PLANNED ANALYSES

This section summarizes major statistical changes in the protocol amendment(s).

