		
collected after surgery will be set to missing and the worst post-baseline value on or before the time of surgery will be used to impute missing Week 24 value (WOCF). For participants with no post-baseline values, the baseline value will be used (hypothetical strategy)."
 
Sensitivity/supplementary analyses updated
	this clinical setting and to update supplementary analyses accordingly
2	23-Feb-2023	
Sample size determination updated.
 
Primary population changed from ITT population to ITT population with screening blood eosinophil count <math>\geq 300</math> cells/mm^3.
 
Statistical hypotheses removed.
 
Multiplicity consideration removed.
 
Multiple imputation removed.
 
Model-based analyses removed.
 
Sensitivity and subgroup analyses removed.
 
Use of descriptive statistics for all endpoints.
	To reflect changes in the study primary objective and endpoint.
		
The intercurrent events handling strategy for taking SCS for any reason prior to Week 24 was changed from 'all data collected after SCS use will be used in the analysis' to 'data after the IE will be set to missing and the worst post-baseline value on or before the time of the IE will be used to impute missing Week 24 value (WOCF)'.
	To change handling of taking SCS for any reason in the primary estimand to an approach more appropriate for this clinical setting.
		
Description of secondary analyses for proportion and time-to-event endpoints removed.
	To reflect changes in the secondary objectives and endpoints.
		
Updated the timing of analyses to only one database lock after all participants have completed the study.
	To reflect the removal of Part B and shortened treatment duration of Part A.

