### ***Disease characteristics at baseline***

The following baseline disease characteristics will be summarized by intervention group:

- Age at onset of CRSsNP (years)
- Time since first diagnosis of CRSsNP (years)
- Baseline LMK score
- Baseline sTSS
- Baseline 3-dimensional CT volumetric measurement of the paranasal sinuses
- Baseline nasal congestion/obstruction score
- Baseline anterior/posterior rhinorrhea score
- Baseline facial pain/pressure severity score
- Baseline loss of smell symptom severity score
- Baseline headache severity score
- Baseline UPSIT score
- Baseline SNOT-22 score
- Baseline rhinosinusitis VAS score
- Baseline EQ-VAS score
- Baseline EQ-5D-5L single index score
- Baseline PGIS score
- Comorbid asthma (Yes, No)

- Baseline FEV1 (L)
- Baseline FEV1 percent predicted (%)
- Baseline ACQ-6 score in participants with comorbid asthma
- Background INCS use
- Smoking history (Never, Former, Current)
- Frequency of alcohol drinking in the past 12 months (never, occasional, at least monthly, at least weekly, at least daily) and number of drinks on a typical day (1 or 2,  $>2$ )
- Screening blood eosinophil count ( $10^9/L$ )
- Screening blood eosinophil count category ( $<0.3$ ,  $\geq 0.3 \times 10^9/L$ )

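### SAP 3.3.2 leaves the collected baseline score out of the two placebo comparisons; adjusting for it is a cheap improvement, not the correction of an error

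*SAP*

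**What the plan says.** SAP 3.3.2 covers the two secondary efficacy comparisons, Week 24 change in LMK and in sTSS, in the ITT population with screening eosinophils of at least 300 cells/mm³. After descriptive statistics by arm it states: "Mean treatment difference (dupilumab vs placebo) and the corresponding 95% CI (based on the t distribution) will be provided". It names no model and no covariate. Protocol 9.4.3 is equally brief: "For endpoints comparing dupilumab to placebo, 95% CI of the treatment difference will be provided".

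The baseline values are available. SAP Appendix 3 lists "Baseline LMK score" and baseline sTSS among the characteristics to be summarised, and SAP 3.1 defines the diary baseline as a 7-day average.

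Leaving out a model is deliberate. SAP Table 7 records, for Amendment 02, "Model-based analyses removed". The protocol's own summary of changes gives the reduced sample size as the reason. Protocol 9.1 adds: "No statistical hypotheses will be tested in this study".

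**The concern.** The primary analysis is a single-arm mean change, so these two contrasts are the only placebo-controlled efficacy estimates among the secondary endpoints. Randomisation is stratified by eosinophil count, INCS use and region, not by baseline LMK or sTSS. At 13 to 15 per arm, a visible difference in baseline score between arms would not be surprising. Where change depends on baseline, that difference feeds into the raw estimate, and the plan has no prespecified way to account for it. An adjustment added after unblinding would be post hoc.

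**Working it through.** **Inputs from the documents.** SAP 4: SD of LMK change 5, 15 per arm with eosinophils ≥300, 10% dropout, so 15 × 0.9 = 13.5 evaluable per arm. Protocol 5.1 (I 02) and SAP 3.2.1: LMK at least 8 at entry, maximum 24.

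**The plan's own figure.** One-arm half-width = t(0.975, n−1) × 5/√n: 3.02 (n = 13), 2.95 (13.5), 2.77 (15). The stated half-width of roughly under 3 reproduces.

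**Raw difference.** Half-width = t(0.975, 2n−2) × 5 × √(2/n): 4.05 (n = 13), 3.88 (14), 3.74 (15).

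**Cost of one covariate.** Residual degrees of freedom fall from 24 to 23 (n = 13) or from 28 to 27 (n = 15). t(0.975, 23)/t(0.975, 24) = 1.002, or 0.2% of width.

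**Assumptions.** The documents give neither the baseline LMK SD (s0) nor the baseline/Week 24 correlation (r). I take s0 = 3.5, 4.0, 4.5 and r = 0.3, 0.5, 0.7, with the change SD held at 5.

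- Week 24 SD: s1 = r·s0 + √(25 − s0²(1 − r²)).
- Slope of change on baseline: b = r·s1/s0 − 1.
- Shift from a 1-SE baseline imbalance at n = 13: b × s0 × √(2/13).

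Example, s0 = 4 and r = 0.5: s1 = 2 + √13 = 5.61; b = 0.5 × 5.61/4 − 1 = −0.30; shift = −0.30 × 4 × 0.392 = −0.47.

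The last two columns come from 20,000 simulated trials per setting, 13 per arm, normal data.

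| r | s0 | s1 | b | Shift | Average width, ANCOVA/raw | Trials with wider ANCOVA interval |
|---|---|---|---|---|---|---|
| 0.3 | 3.5 | 4.77 | −0.59 | −0.81 | 0.93 | 24% |
| 0.3 | 4.0 | 4.43 | −0.67 | −1.05 | 0.87 | 9% |
| 0.3 | 4.5 | 3.91 | −0.74 | −1.30 | 0.77 | 2% |
| 0.5 | 3.5 | 5.73 | −0.18 | −0.25 | 1.02 | 74% |
| 0.5 | 4.0 | 5.61 | −0.30 | −0.47 | 0.99 | 56% |
| 0.5 | 4.5 | 5.38 | −0.40 | −0.71 | 0.96 | 33% |
| 0.7 | 3.5 | 6.78 | +0.36 | +0.49 | 0.99 | 54% |
| 0.7 | 4.0 | 6.90 | +0.21 | +0.33 | 1.01 | 68% |
| 0.7 | 4.5 | 6.98 | +0.09 | +0.15 | 1.02 | 77% |

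The median absolute shift is 0.49. The 95th percentile of the width ratio is 0.95 to 1.09, so a single interval can be about 10% wider. At 15 per arm the average ratios are 0.76 to 1.02. The r = 0.7 rows are the least plausible: their Week 24 SD is close to that of a uniform spread over 0–24 (7.2).

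**How often imbalance matters.** A baseline difference of 1 SE or more occurs in about 32% of randomised trials at any sample size. One above 1.5 SE occurs in about 13%. Within that 13%, raw-interval coverage is about 81–90% at r = 0.3 and 92–94% at r = 0.5 and 0.7, while ANCOVA stays at about 94–96%.

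**How well one trial can correct.** SE of the slope is approximately s1·√(1 − r²)/(s0·√24). In three settings |b| is below it: 0.18 against 0.29, 0.21 against 0.25, and 0.09 against 0.23. The estimated slope then has the wrong sign in about 27%, 20% and 35% of trials.

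**Validity.** ANCOVA coverage is 94.8–95.2% with normal data. After surgery or SCS, SAP 3.2.2 says "For participants with no post-baseline values, the baseline value will be used". Since the only scheduled CTs up to Week 24 are at screening and Week 24, that will often mean a change of exactly zero. With an assumed 15% of zero changes per arm, coverage is 94.8–95.3% and the average ratios are 0.83–1.02. With integer LMK (baseline 8–24, Week 24 0–24), mean change −4 against −1 and 10% against 20% zero changes (all assumed), coverage is 94.7–95.2% and the ratios are 0.82–1.03.

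**sTSS.** No SD is stated, and a 7-day baseline average is compared with a 28-day Week 24 average, so no figure can be given.

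**The case against.** The strongest reply is that this is a documented choice between two valid estimators. Amendment 02 moved every endpoint to descriptive statistics, SAP 3.3.2 follows Protocol 9.4.3, nothing is tested, and the raw t interval already allows for chance imbalance averaged over randomisations. In six of the nine settings average width changes only by −4% to +2%, and in five of those six the adjusted interval is wider in most single trials. All of that stands, and it rules out calling the plan wrong.

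The small-sample reason is less persuasive against this particular change. It tells against models with several covariates and against multiple imputation, but not against one continuous covariate costing one degree of freedom.

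A reader might infer that adjustment would reliably tighten the interval. With equal baseline and Week 24 SDs the gain at 13 per arm would be 17%, 11% and 6% for r = 0.3, 0.5 and 0.7. The documents do not support relying on that. Equal SDs with a change SD of 5 imply a baseline SD of 5/√(2(1 − r)), which is 5.0 at r = 0.5 and 6.5 at r = 0.7. A uniform spread over the eligible 8–24 range has an SD of only 4.9.

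A reader might also infer that imbalance is likely and that ANCOVA removes its effect. A 1-SE imbalance has a probability of about one in three, and with 26 participants the estimated slope corrects for it only approximately.

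**Conclusion.** The point holds as a cheap improvement. The raw difference is unbiased under randomisation, its interval is valid, no decision rests on it, and neither the single-arm primary estimate nor the sample-size statement is affected. Reading the omission as a bias, an invalid interval or an oversight would go beyond the documents.

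The main benefit is prespecified protection against chance baseline imbalance. For LMK this is worth 0.2 to 1.3 points per 1 SE of imbalance (median 0.5), against a half-width near 4. It works on average; in one trial it can go the wrong way when the true slope is near zero. The shift is regression to the mean only where the slope is negative (r = 0.3 and 0.5). Precision is secondary: more than 5% narrower only at r = 0.3, otherwise roughly unchanged. These sizes rest on the assumed baseline SD and correlation. For sTSS the argument is qualitative only.

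**What to change.** In SAP 3.3.2, before database lock and while treatment is blinded, prespecify an ANCOVA of change on treatment and that endpoint's own baseline value, separately for LMK and sTSS. Report the adjusted difference with its t-based 95% CI, and keep the raw arm means and raw difference alongside.

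SAP 3.4.3 takes over the secondary-endpoint approach, so state there whether its analyses follow the adjusted or the raw version. Record the departure from the descriptive approach of Protocol 9.4.3 in SAP 3.9, which at present lists only changes made by the amendments. SAP 3.4.2, intercurrent-event handling and the single-arm primary analysis stay as written, so the placebo comparisons in 3.4.2 remain raw.

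Cost: two models plus any that 3.4.3 adds, one residual degree of freedom per model, a few sentences in the SAP, and the chance that a single LMK interval comes out about 10% wider. No new data or participants are needed.

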5.4 Screen Failures	Added the below sentence: All other screening procedures must be repeated for rescreening.	To clarify to participating clinical sites that in case of rescreening all procedures need to be repeated, except CT scan if within the defined window period.
6.1 Study Intervention(s) Administered	Addition of the following sentence: 'During study visits, the IMP is administered on sites after all procedures.'	In order to further clarify that IMP will be administered at sites at the time of Visits.
6.5.3 Rescue medicine	Changed from Short course OCS (prednisone or equivalent prednisolone up to 7 days; avoid use 4 weeks before Week 24 or Week 52, where applicable). To Short course OCS (prednisone or equivalent prednisolone up to 14 days; avoid use 4 weeks before Week 24 or Week 52, where applicable).	To clarify an inconsistency between Prohibited medications and Rescue medications, the short course of OCS is up to 14 days.

Section # and Name	Description of Change	Brief Rationale
8.6 Pharmacodynamics	Removed measurement of secreted P-glycoprotein.	Test is unable to be performed by the Sponsor due to assay limitations.
9.2 Sample size determination 9.3 Populations for analyses	Sample size determination updated. Primary population changed from ITT population to ITT population with screening blood eosinophil count $\geq 300$ cells/mm  .	To reflect changes in the study primary objective and endpoint.
9.1 Statistical hypotheses 9.4.1 General considerations 9.4.2 Primary endpoint(s)	Statistical hypotheses removed. Multiplicity consideration removed. Multiple imputation removed. Model-based analyses removed. Sensitivity and subgroup analyses removed. Use of descriptive statistics for all endpoints.	To apply more appropriate analysis methods based on the reduced sample size.
9.4.2 Primary endpoint(s)	The intercurrent events handling strategy for taking SCS for any reason prior to Week 24 was changed from 'all data collected after SCS use will be used in the analysis' to 'data after the IE will be set to missing and the worst post-baseline value on or before the time of the IE will be used to impute missing Week 24 value (WOCF)'.	To change handling of taking SCS for any reason in the primary estimand to an approach more appropriate for this clinical setting.

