## 4 STUDY DESIGN

### 4.1 OVERALL DESIGN

This is a Phase 2 multicenter study to evaluate the efficacy and safety of dupilumab, in participants with uncontrolled CRSsNP. This is a randomized, double-blind, placebo-controlled study in adult participants regardless of screening eosinophil count to evaluate the treatment effect of dupilumab on sinus opacification as assessed by the LMK sinus CT scan total score and to provide data on safety.

All participants (adults only) will enter a screening period (2 to 4 weeks), with a 24 to 52-week treatment period, followed by post-treatment follow-up (12 weeks).

Approximately 70 adult participants will be randomized 1:1 (approximately 35 participants per arm) into 2 treatment groups as follows:

- Arm A: Dupilumab 300 mg q2w,
- Arm B: Matching placebo.

Randomization will be stratified by screening blood eosinophil count ( $\geq 300$  cells/mm $^3$  or  $< 300$  cells/mm $^3$ ), background INCS use (yes or no) and region.

To ensure enrollment according to the intended distribution of screening blood eosinophil count, alerts will be built into the IRT to control the number of participants in each stratification group as follows:

- $\geq 300$  cells/mm $^3$ : approximately 15 participants per arm,
- $< 300$  cells/mm $^3$ : approximately 20 participants per arm.

*Note: The treatment will stop for all participants when the LPI has completed 24 weeks of treatment. Therefore, all participants following Amendment 02 will be treated for at least 24 weeks and the other participants (enrolled before Amendment 02) will have variable treatment period and may continue up to 52 weeks.*

In addition, in order to have an adequate number of participants with comorbid asthma, alerts will be built into the IRT to limit the number of participants without comorbid asthma to no more than 70% of the randomized population.

During the study, participants who report deterioration requiring medical/surgical intervention may come to the site for clinical evaluation. An unscheduled visit may be used for this purpose and, if necessary, the Investigator may consider one of the treatment alternatives described in [Section 6](#).

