## 1 INTRODUCTION

### 1.1 STUDY DESIGN

This is a Phase 2, randomized, double-blind, placebo-controlled study to evaluate the efficacy and safety of dupilumab in adult participants with uncontrolled chronic rhinosinusitis without nasal polyposis (CRSsNP).

After a screening period of 2 to 4 weeks, approximately 70 participants will be centrally randomized (using permuted block randomization schedule) via Interactive Response Technology (IRT) in a 1:1 ratio to dupilumab 300 mg q2w or placebo. Randomization will be stratified by screening blood eosinophil count ( $\geq 300$  cells/mm $^3$  or  $< 300$  cells/mm $^3$ ), background intranasal corticosteroids (INCS) use (yes or no) and region. To ensure enrollment according to the intended distribution of screening blood eosinophil count, the number of participants in each stratification group will be controlled as follows:

- $\geq 300$  cells/mm $^3$ : approximately 15 participants per arm,
- $< 300$  cells/mm $^3$ : approximately 20 participants per arm.

In addition, in order to have an adequate number of participants with comorbid asthma, the number of participants without comorbid asthma will be limited to no more than 70% of the randomized population.

The study has a 24 to 52-week treatment period. Study treatment will stop for all participants when the last participant has completed 24 weeks of treatment. Therefore, all participants following protocol amendment 02 will be treated for at least 24 weeks and the other participants (enrolled before amendment 02) will have a variable treatment period which may be up to 52 weeks.

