### 3 STATISTICAL ANALYSES

#### 3.1 GENERAL CONSIDERATIONS

In general, continuous data will be summarized using the number of observations available, mean, standard deviation (SD), median, minimum, and maximum. Categorical and ordinal data will be summarized using the count and percentage of participants. The summary statistics will be provided at each visit, including data collected beyond Week 24.

The baseline value of efficacy parameters is defined as the last available value up to randomization date and prior to the first dose of study medication unless otherwise specified. The baseline value of the other parameters is defined as the last available value prior to the first dose of investigational medicinal product (IMP) if the participant is treated, or the last available value up to randomization date if the participant is not exposed to IMP.

For endpoints collected on the daily CRSsNP sinonasal symptom diary, baseline is defined as the average of the scores in the 7 days prior to randomization. If there are less than 7 but at least 4 non-missing scores available, the baseline score is the average of the available scores in the 7 days. If there are less than 4 non-missing scores, then baseline will be the average of the most recent 4 days with non-missing scores prior to randomization.

Stratification factors used in analyses will be derived based on eCRF data (for background INCS and region) or central laboratory data (for screening blood eosinophil count).

Unless otherwise specified, analyses will be performed by intervention group and overall for baseline and demographics characteristics.

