## 4 SAMPLE SIZE DETERMINATION

Sample size calculation was performed to ensure reasonable accuracy for the estimation of the primary endpoint in participants treated with dupilumab with screening blood eosinophil count  $\geq 300$  cells/mm $^3$ . With a 1:1 randomization ratio, a standard deviation (SD) of 5 and a dropout rate of 10%, a sample size of approximately 30 participants (15 per arm) with screening blood eosinophil count  $\geq 300$  cells/mm $^3$  will provide a half-width of approximately less than 3 for the 2-sided 95% CI in the dupilumab group which is deemed reasonable.

In addition, it is planned to include approximately 40 participants (20 per arm) with screening blood eosinophil count  $< 300$  cells/mm $^3$ . Thus, the planned total sample size is approximately 35 participants per arm.

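### The dupilumab–placebo intervals ignore background INCS use, a stratification factor; they remain valid but are wider than needed if INCS use relates to change

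*SAP*

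**What the plan says.** SAP 1.1 describes permuted-block randomisation stratified by screening eosinophil count, "background intranasal corticosteroids (INCS) use (yes or no) and region". Protocol 4.1 names the same factors: "background INCS use (yes or no) and region".

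For the two efficacy secondary endpoints, LMK and sTSS, in participants with eosinophils of at least 300 cells/mm³, SAP 3.3.2 states: "Mean treatment difference (dupilumab vs placebo) and the corresponding 95% CI (based on the t distribution) will be provided". SAP 3.4.2 uses the same form for the exploratory endpoints compared between arms. Neither section names a covariate or a stratum.

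SAP 3.1 gives a source for the factors: "Stratification factors used in analyses will be derived based on eCRF data (for background INCS and region", with eosinophil count taken from the central laboratory. In the legible text, the eosinophil factor then defines the analysis population. INCS use and region appear only in the baseline tables.

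The plain analysis is a deliberate choice. SAP Table 7 records under amendment 02: "Model-based analyses removed". The protocol's summary of changes gives the reason: "To apply more appropriate analysis methods based on the reduced sample size".

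**The concern.** Stratified permuted blocks roughly equalise INCS use between the arms, so INCS contributes less to the true variability of the treatment difference than it would under simple randomisation. A two-sample t interval does not credit this: differences in outcome between INCS users and non-users remain in the residual variance. If INCS use relates to change, the reported interval is wider than the design warrants. With about 27 evaluable participants, incomplete blocks and dropout also leave some chance INCS imbalance, which the raw difference does not correct.

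The LMK and sTSS differences are the only non-exploratory randomised efficacy comparisons in the primary population, because the primary endpoint is summarised in the dupilumab arm alone. The LMK half-width is already near 4 points on a 24-point scale, so a cheap gain in precision is worth considering.

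**Working it through.** **Inputs from the documents.** SAP 4 gives "a standard deviation (SD) of 5 and a dropout rate of 10" percent and "a sample size of approximately 30 participants (15 per arm) with screening blood eosinophil count" of at least 300. Evaluable per arm: 15 × 0.90 = 13.5, or 27 in total.

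**Inputs not in the documents (assumed).** R², the share of within-arm variance in change explained by INCS use; the share of INCS users; block size 4; four equally likely regions (SAP 5.3 lists four).

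**1. The plan's own figure.** The one-arm half-width is t(0.975, n−1) × SD/√n. At n = 13.5 it is 2.95 (2.89 at n = 14, 3.02 at n = 13). The stated precision of approximately less than 3 is reproduced.

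**2. Unadjusted difference.** t(0.975, 25) × 5 × √(2/13.5) = 2.060 × 1.924 = 3.96.

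**3. Adjusted for INCS, strata exactly balanced.** The half-width is t(0.975, 24) × 5 × √(1−R²) × √(2/13.5), with t = 2.064.

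| R² | Half-width | Against 3.96 |
|---|---|---|
| 0 | 3.97 | +0.2% |
| 0.02 | 3.93 | −0.8% |
| 0.05 | 3.87 | −2.3% |
| 0.10 | 3.77 | −4.9% |
| 0.20 | 3.55 | −10.4% |

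Break-even here is R² = 1 − (t(25)/t(24))², about 0.4%.

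**4. Allowing for chance imbalance.** Simulation: 30 participants, permuted blocks within INCS × region, 10% random dropout, 5,000 runs per setting.

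| INCS users | R² | Unadjusted | Adjusted | Ratio |
|---|---|---|---|---|
| 50% | 0 | 3.950 | 3.985 | 1.009 |
| 50% | 0.022 | 3.946 | 3.933 | 0.997 |
| 50% | 0.059 | 3.953 | 3.865 | 0.978 |
| 50% | 0.138 | 3.959 | 3.703 | 0.935 |
| 50% | 0.265 | 3.980 | 3.432 | 0.862 |
| 70% | 0 | 3.953 | 3.995 | 1.010 |
| 70% | 0.019 | 3.967 | 3.971 | 1.001 |
| 70% | 0.050 | 3.963 | 3.903 | 0.985 |
| 70% | 0.118 | 3.959 | 3.750 | 0.947 |
| 70% | 0.232 | 3.957 | 3.482 | 0.880 |
| 90% | 0 | 3.945 | 4.012 | 1.017 |
| 90% | 0.022 | 3.962 | 3.982 | 1.005 |
| 90% | 0.054 | 3.940 | 3.901 | 0.990 |
| 90% | 0.115 | 3.947 | 3.780 | 0.958 |

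The cost at R² = 0 is therefore 0.9% to 1.7%. Linear interpolation puts break-even near 1.6%, 2.1% and 3.3% for 50%, 70% and 90% users. Allowing for simulation error, I take 2% to 4%. Interpolating to R² = 0.10 gives about 4.4%, 4.3% and 3.4% narrower, against 4.9% with exact balance; at 0.20 it gives about 10% for both 50% and 70% users. With 90% users, about 6% of runs contained only one INCS level. In those runs no term could be fitted and the unadjusted interval was used.

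**5. Coverage.** Unadjusted coverage was 94.3% to 96.2% across settings, with simulation standard error √(0.95 × 0.05/5000) = 0.3 points. With 50% users it reached 96.0% to 96.2% at R² of 0.14 to 0.27. That is nominal to slightly conservative.

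**6. Region.** Adding region to INCS uses 4 df. The multiplier rises by t(21)/t(25) = 2.080/2.060, about 1%, before imbalance. Simulated with 60% users, the total cost was about 3% when neither factor mattered, with break-even only between 5% and 10% of variance.

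**7. sTSS.** The documents give no SD, so no half-width in points follows. The percentages do not depend on the SD and carry over for the same number evaluable and the same R².

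**The case against.** The strongest defence is that the sponsor chose this. Amendment 02 moved every endpoint to descriptive statistics because of the smaller sample, Protocol 9.1 tests no hypothesis, and a t interval for a randomised difference is valid. That stands as a defence of validity. It does not rule out one binary term costing 1 of about 25 df.

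Second, nothing in the documents shows that INCS use predicts change. Users must be on a stable dose before screening and are to keep it (Protocol 5.2, 6.5.1), so their baseline is already measured on INCS. This stands, and it is why the gain is only conditional. A link is plausible, since starting or changing INCS spray is listed as rescue (Protocol 6.5.3) and data after such rescue are kept, but its size is unknown.

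Third, a small effect brings little. A further simulation (8,000 runs, same assumed blocks and regions) gave a mean gain at R² = 5% of only 0.9% to 1.7%, or 0.04 to 0.07 LMK points, and the adjusted interval was wider in 50% to 53% of individual trials. This also stands.

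Fourth, region is a stratifier too, so leaving it out looks inconsistent. The distinction rests on degrees of freedom (step 6), not on design principle, and should be stated as such.

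Fifth, INCS use is tabulated by arm at baseline (SAP 5.3). That would show an imbalance but not correct for it.

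**Conclusion.** The point holds as a minor, conditional loss of precision. The between-arm intervals in SAP 3.3.2 and 3.4.2 leave out a two-level factor that the trial randomises by. For LMK the effect of including it runs from about 1% to 2% wider if INCS explains nothing, through break-even at about 2% to 4% of variance, to about 4% to 5% narrower at 10% (nearer 3.5% if 90% use INCS) and about 10% narrower at 20%. This rests on the SAP's SD and dropout and on the assumed INCS share, block size and regional split.

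A reader might infer more than the documents support:

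- That the intervals are invalid or biased. They are not; coverage stays close to or slightly above nominal.
- That adjustment is free, or always costs under 1%. Chance imbalance raises the cost to as much as about 2%.
- That LMK is the only randomised efficacy estimate in the primary population. sTSS and the exploratory endpoints are also compared by arm there.
- That an eosinophil term is missing. The legible between-arm analyses sit within one eosinophil stratum, and the all-ITT LMK and sTSS analyses use dupilumab only.
- That the primary result is affected. Its single-arm interval involves no between-arm comparison.

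**What to change.** In SAP 3.3.2, and in SAP 3.4.2 where arms are compared on continuous change endpoints, estimate the treatment difference and its t-based 95% CI from a linear model with treatment and background INCS use (yes/no, from the eCRF as SAP 3.1 already provides). Drop the INCS term if only one level is observed. Keep the raw means and the unadjusted interval as descriptive output. Leave four-level region out at this sample size and say why. State in SAP 3.1 which stratification factors enter which analyses, and record the change in SAP 3.9, since amendment 02 removed models. Settle this before unblinding.

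The cost is a few lines of SAP text, one model term and 1 df, with about 1% to 2% more width if INCS use is unrelated to outcome. If the sponsor prefers the plain interval, the minimum is a sentence in SAP 3.1 saying that INCS use and region do not enter the between-arm comparisons, and why.
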